5.4.4 Vital signs

Baseline is defined as the last valid assessment value prior to dosing.

The measured values of each of vital signs at baseline and different time points after baseline were described and analyzed, and the changes in measured results of each vital sign at different time points after baseline relative to baseline were given.

Results for vital signs were tabulated separately for each vital sign parameter by patient and visit.

5.4.5 Other safety measurements

Other safety measurements were collected according to clinical indications. However, only pulmonary function test and chest CT assessment data were recorded in CRF, and other data was only be kept in the source file.

The assessment data of pulmonary function test and chest CT were tabulated by patient only and not summarized in tables.

5.5 Efficacy analyses (secondary analyses)

All efficacy analyses were based on FAS.

5.5.1 Overall Survival (OS)

Overall survival is defined as time from study treatment to death due to any cause.

If a patient was alive at the data cutoff, the last known survival date was used as the censored date for analysis. The definition of the last known survival date is detailed in Section 5.4.2.4.1.

If the data permits, the Kaplan-Meier method was used to obtain the survival function estimate and the median OS estimate, the survival curve was plotted, and the error of the survival function was estimated using the Greenwood formula [1], resulting in a 95% confidence interval

of the median OS. In addition, the survival probabilities and their 95% confidence intervals at different time points such as at Month 3 and Month 6 were also calculated.

5.5.2 Progression-Free Survival (PFS)

Progression-free survival is defined as time from the start of study treatment to progression of disease (PD) or death due to any cause (whichever occurs first).

Time to progression of disease is defined as the time when progression is first observed:

- At least a 20% increase in the sum of diameter of all measured target lesions, taking as reference the smallest sum of diameter of all target lesions recorded at or after baseline. In addition to the relative increase of 20%, the sum must also demonstrate an absolute increase of 5 mm;

Or

- Unequivocal progression of existing non-target lesions;

Or

- Emergence of new lesions.

The calculation of PFS was based on the date of the imaging examination, not the date of the RECIST tumor evaluation or the date of the visit.

For calculation of PFS, if imaging examinations were completed on multiple dates, the progression date or censored date was determined according to the following rules:

- For patients with progression of disease, the date of progression is defined as the earliest date when it is assessed that there is progression.
- For patients without progression of disease, the censored date is defined as the date of the latest imaging examination within the visit.

If the patient was alive and progression-free at the time of data cutoff, the date of the last imaging examination of the measurable lesion was used as the date of the last evaluation in the PFS analysis, i.e., the censored date. If the patient had no PFS data available or was missing baseline data assessment and was still alive at the data cutoff, the study treatment start date was used as the censored date in the PFS analysis. Detailed censoring rules for PFS are shown in Table 2.

Table 2 Censoring rules for PFS

#	Situation	Progression or censored date	Result
1	No baseline or post-baseline tumor assessment	Study treatment start date	Censored
2	Documented progression of disease	Progression date	Progression
3	No progression based on RECIST assessment (i.e. clinical progression based on investigator's assessment) leading to end of treatment	Date of discontinuation of treatment	Progression
4	No events occurred	Date of last adequate tumor assessment	Censored
5	Initiation of new anti-cancer therapy	Date of last adequate tumor assessment prior to initiation of subsequent anticancer therapy (start date of the	Censored

		study treatment if there is no post-baseline imaging examination)	
6	Death ^a	Date of death	Progression
7	Event ^b documented after two or more missing tumor assessments	Date of last adequate tumor assessment prior to two or more consecutive tumor assessments not performed as per protocol	Censored

Note 1: Adequate assessment included tumor assessment in the following situations: CR, PR, SD, PD
Note 2: ^a Including cases where no tumor evaluation was conducted after enrollment and death occurred during two consecutive scheduled tumor evaluation visits (i.e., date of death is less than or equal to 24 weeks + 2 weeks from the start date of study treatment).
Note 3: ^b Indicating that the date of death or progression of disease is greater than 24 weeks + 2 weeks from the last tumor assessment.

New anticancer therapy is defined as the following drugs received at or after the start of study treatment:

- The name of the drug is Capecitabine, Temozolomide, or Sandostatin LAR
- Indication or reason for administration is chemotherapy or anti-tumor

Baseline is defined as the last RECIST1.1 assessment prior to the start of study treatment.

PFS was analyzed using statistical methods similar to those used for OS analysis.

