14.1.6 Methods of tumor measurement - general guidelines

In this document, the term “contrast” refers to intravenous (i.v) contrast.

The following considerations are to be made when evaluating the tumor:

- All measurements should be taken and recorded in metric notation (mm), using a ruler or calipers. All baseline evaluations should be performed as closely as possible to the beginning of treatment and never more than 4 weeks before the beginning of the treatment.
- Imaging-based evaluation is preferred to evaluation by clinical examination when both methods have been used to assess the antitumor effect of a treatment.
- For optimal evaluation of patients, the same methods of assessment and technique should be used to characterize each identified and reported lesion at baseline and during follow-up. Contrast-enhanced CT of chest, abdomen and pelvis should preferably be performed using a 5 mm slice thickness with a contiguous reconstruction algorithm. CT/MRI scan slice thickness should not exceed 8 mm cuts using a contiguous reconstruction algorithm. If, at baseline, a patient is known to have a medical contraindication to CT contrast or develops a contraindication during the trial, the following change in imaging modality will be accepted for follow up: a non-contrast CT of chest (MRI not recommended due to respiratory artifacts) plus contrast-enhanced MRI of abdomen and pelvis.

- A change in methodology can be defined as either a change in contrast use (e.g. keeping the same technique, like CT, but switching from with to without contrast use or vice-versa, regardless of the justification for the change) or a change in technique (e.g. from CT to MRI, or vice-versa), or a change in any other imaging modality. A change in methodology will result by default in a UNK overall lesion response assessment. However, another response assessment than the Novartis calculated UNK response may be accepted from the investigator or the central blinded reviewer if a definitive response assessment can be justified, based on the available information.
- **FDG-PET:** can complement CT scans in assessing progression (particularly possible for ‘new’ disease). New lesions on the basis of FDG-PET imaging can be identified according to the following algorithm:
 - Negative FDG-PET at baseline, with a positive FDG-PET at follow-up is a sign of PD based on a new lesion.
 - No FDG-PET at baseline with a positive FDG-PET at follow-up:

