14.1.19 Progression-free survival

Usually in all Oncology studies, patients are followed for tumor progression after discontinuation of study medication for reasons other than progression or death. If this is not used, e.g. in Phase I or II studies, this should be clearly stated in the protocol. Note that randomized trials (preferably blinded) are recommended where PFS is to be the primary endpoint.

Progression-free survival (PFS) is the time from date of randomization/start of treatment to the date of event defined as the first documented progression or death due to any cause. If a patient has not had an event, progression-free survival is censored at the date of last adequate tumor assessment.

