14.1.25 Definition of start and end dates for time to event variables

Assessment date

For each assessment (i.e. evaluation number), the **assessment date** is calculated as the latest of all measurement dates (e.g. X-ray, CT-scan) if the overall lesion response at that assessment is CR/PR/SD/UNK. Otherwise - if overall lesion response is progression - the assessment date is calculated as the earliest date of all measurement dates at that evaluation number.

Start dates

For all “time to event” variables, other than duration of response, the randomization/ date of treatment start will be used as the start date.

For the calculation of duration of response the following start date should be used:

- Date of first documented response is the assessment date of the first overall lesion response of CR (for duration of overall complete response) or CR / PR (for duration of overall response) respectively, when this status is later confirmed.

End dates

The end dates which are used to calculate ‘time to event’ variables are defined as follows:

- Date of death (during treatment as recorded on the treatment completion page or during follow-up as recorded on the study evaluation completion page or the survival follow-up page).
- Date of progression is the first assessment date at which the overall lesion response was recorded as progressive disease.
- Date of last adequate tumor assessment is the date the last tumor assessment with overall lesion response of CR, PR or SD which was made before an event or a censoring reason occurred. In this case the last tumor evaluation date at that assessment is used. If no post-baseline assessments are available (before an event or a censoring reason occurred) the date of randomization/start of treatment is used.
- Date of next scheduled assessment is the date of the last adequate tumor assessment plus the protocol specified time interval for assessments. This date may be used if back-dating is considered when the event occurred beyond the acceptable time window for the next tumor assessment as per protocol (see [Section 14.1.26](#)).

Example (if protocol defined schedule of assessments is 3 months): tumor assessments at baseline - 3 months - 6 months - missing - missing - PD. Date of next scheduled assessment would then correspond to 9 months.

- Date of discontinuation is the date of the end of treatment visit.

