5.5.5 Additional analysis for assessment the impact of COVID-19

Considering that the outbreak of COVID-19 in 2020 has affected the work of each study site to varying degrees, protocol deviations due to COVID-19 were collected for this study, including visit assessments completed at other hospitals, visit assessments and tests not completed or out-of-window due to COVID-19, changes in drug supply methods, interruption or discontinuation of study drug treatment, etc. Patients seriously affected by COVID-19 were identified at the data review meeting, and patients whose response was seriously affected by COVID-19 were excluded from the sensitivity analysis of efficacy, with the purpose of exploring the potential impact of COVID-19 on the efficacy assessment results of this study.

6 Interim analysis

Interim analysis was conducted during the study as needed. In order to obtain an outline of the data submitted to the China Food and Drug Administration when the drug license was renewed in February 2018, the project team planned to conduct the first interim analysis around July 2017. Moreover, during the study, based on the requirements of the Center for Drug Evaluation, clinical data was submitted every 5 years for license renewal, so the project team planned to conduct the second interim analysis in February 2021.

The contents of the interim analysis included all primary and secondary endpoints covered by the statistical analysis plan. The analytical methods of this study are predominantly descriptive, so alpha spending function is not applicable. For interim analysis, data will be analyzed according to the content and methods of analysis described in this SAP, and there is no plan to formulate a separate SAP of interim analysis.

7 Modification of the Analytical Method for the Protocol Plan

None.

8 Statistical Analysis Form Template Statistics

The analysis form template will be provided in a separate document.

9 Reference

1. Collett, D. (2003), Modeling Survival Data in Medical Research, Second Edition, London: Chapman & Hall.

10 Appendix

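### SAP 5.5.2 gives two censoring dates for PFS in patients alive and progression-free at cut-off: the last scan of the measurable lesion (text) and the last adequate assessment (Table 2 and protocol)

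*SAP*

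**What the plan says.** SAP 5.5.2 deals twice with the patient who is alive and progression-free at cut-off.

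- **Text:** "the date of the last imaging examination of the measurable lesion was used as the date of the last evaluation in the PFS analysis". That date is the censoring date, and no response category is required.
- **Table 2, row 4 (no events):** "Date of last adequate tumor assessment". Note 1 explains: "Adequate assessment included tumor assessment in the following situations: CR, PR, SD, PD". UNK is not in the list.

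The two are linked only by the sentence "Detailed censoring rules for PFS are shown in Table 2", which does not say that the table prevails.

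The protocol has one rule. Under 14.1.19, for a patient without an event, "progression-free survival is censored at the date of last adequate tumor assessment". Section 14.1.25 dates this by "the last tumor assessment with overall lesion response of CR, PR or SD which was made before an event or a censoring reason occurred". Section 14.1.39 adds that having only UNK assessments just before cut-off comes under the censoring reason that adequate assessment is no longer available. SAP section 7 declares no change from the protocol's methods.

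**The concern.** The text and the table agree unless the last scan was performed but could not be rated CR, PR or SD. The protocol shows how this can happen although the measurable lesion was imaged:

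- Section 14.1.6: "A change in methodology will result by default in a UNK overall lesion response assessment".
- Table 14-3: a target response of CR, PR or SD with an UNK non-target response gives an overall UNK.

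By the protocol's own definition, such a scan does not establish that the patient was still progression-free. The text nevertheless credits follow-up up to it. PFS is one of only two secondary endpoints, and protocol 2.2 chose it to match the primary endpoint of the phase III pNET study, so its censoring date should have one definition.

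**Working it through.** The plan states no figure that depends on this rule. The design is single-arm and descriptive, and the sample size rests on feasibility.

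**1. Dates for individual patients.** Scans fall every 12 weeks (SAP Appendix 1, footnote e), and 12 × 7 = 84 days. With treatment start as day 1 (SAP 5.1.1), scan k falls on day 84k + 1: days 85, 169 and 253 for weeks 12, 24 and 36.

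| Ratings, then cut-off | Text rule | Table 2 / protocol rule | Difference |
|---|---|---|---|
| SD, SD, UNK | day 253 | day 169 | 84 days (2.76 months) |
| SD, UNK, UNK | day 253 | day 85 | 168 days (5.52 months) |
| UNK only | day 85 | day 1 | 84 days (2.76 months) |

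Months are days / 30.4375. The last line applies the fallback to treatment start in protocol 14.1.25. Every line assumes that the measurable lesion was imaged at the UNK scan. If it was not, the text rule does not move the date either.

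**2. Direction.** The events are the same under both rules. At each event time the text rule keeps at least as many patients at risk, so each factor 1 − d/n of the Kaplan-Meier product is equal or larger. The text-rule curve is therefore never below the other.

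**3. Size.** An illustrative simulation used 60 patients and 1,000 replicates. Its assumptions were:

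- exponential PFS with median 11.04 months (everolimus arm of the phase III pNET study, protocol 1.2.1.2);
- 12-weekly scans, with progression dated at the first rated scan that shows it;
- exponential time to end of scanning with median 12 or 24 months;
- each scan UNK with a fixed probability, the measurable lesion always imaged;
- Table 2, row 7, not applied.

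| Median time to end of scanning | UNK rate | Patients with different dates (mean) | Median PFS, text vs table (months) | Difference (months) | 12-month PFS, text vs table | Replicates in which the median differs |
|---|---|---|---|---|---|---|
| 12 months | 5% | 1.3 | 12.97 vs 12.88 | 0.09 | 50.2% vs 49.9% | 2.5% |
| 12 months | 10% | 2.8 | 13.25 vs 13.02 | 0.23 | 51.3% vs 50.6% | 7.6% |
| 12 months | 20% | 5.4 | 13.42 vs 13.02 | 0.40 | 52.1% vs 50.7% | 13.0% |
| 12 months | 30% | 8.3 | 14.12 vs 13.33 | 0.79 | 54.1% vs 51.9% | 23.7% |
| 24 months | 5% | 1.0 | 12.88 vs 12.81 | 0.07 | 50.4% vs 50.2% | 2.4% |
| 24 months | 10% | 1.9 | 13.00 vs 12.89 | 0.11 | 51.0% vs 50.7% | 4.1% |
| 24 months | 20% | 3.9 | 13.42 vs 13.19 | 0.23 | 52.4% vs 51.7% | 7.9% |
| 24 months | 30% | 6.0 | 14.02 vs 13.64 | 0.38 | 54.4% vs 53.2% | 12.7% |

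Both medians exceed 11.04 months mainly because progression is seen only at a scheduled scan. The difference between the rules is what matters here.

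**The case against.** The best defence is that the documents nearly settle the question. The text sends the reader to Table 2 for the detailed rules, and protocol 14.1.19, 14.1.25 and Table 14-5 (situation D) all agree with row 4. Just before the disputed sentence, the SAP explains that PFS is dated by imaging rather than by evaluation or visit. In that setting the sentence may only say which calendar date stands for the last evaluation, and a programmer would probably follow Table 2. This lowers the importance of the point. It does not remove the conflict, because the sentence as written sets no condition on the rating and no order of precedence is stated.

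Four stronger readings are tempting, and the documents do not carry them.

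- **UNK is frequent.** No rate is given. Protocol 14.1.6 lets the investigator justify a definitive response instead of UNK, 14.1.32 allows UNK assessments to be re-evaluated, and protocol 7.2.1 and SAP Appendix 1 call for the same type of scan throughout. SAP 5.5.5 mentions "visit assessments completed at other hospitals" but does not say that the imaging method changed there. It also plans a sensitivity analysis without patients whose response was seriously affected by COVID-19.
- **The conflict can turn a censored patient into an event.** The text and row 4 both concern patients without an event, so only the date can move.
- **Note 3 lets UNK scans reverse the outcome under row 7.** Take SD at week 24, UNK at weeks 36 and 48, and PD at week 60. The gap is 60 − 24 = 36 weeks from the last adequate assessment, above the 26-week limit, but 60 − 48 = 12 weeks from the last scan performed. Row 7, however, concerns assessments that were missing or not performed, and these scans were performed. Whether it applies is unclear, and excluding UNK there could discard a documented progression.
- **Listing PD in Note 1 distorts the result.** It differs from protocol 14.1.25 but has no practical effect, since a documented PD is already an event under row 2.

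**Conclusion.** The inconsistency is real and minor. The SAP text states a censoring rule that differs from its own Table 2 and from the protocol, and SAP section 7 does not declare the departure. Following the text adds 84 days of censored follow-up for each UNK scan at the end of a patient's series, provided that the measurable lesion was imaged. Under the simulation's assumptions the median rises by about 0.1 month at 5% UNK and by 0.4 to 0.8 month at 30%. The 12-month estimate rises by 0.2 to 2.2 percentage points over the whole range tried. At 5% UNK the median itself changed in fewer than 3% of replicates, so it would be too strong to say that median PFS hinges on this sentence. PFS is secondary and descriptive, so no error rate or power is affected. The Note 3 wording is a separate ambiguity, not a demonstrated error.

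**What to change.** In the text of SAP 5.5.2, replace the rule for patients alive and progression-free at cut-off with: the date of the last adequate tumor assessment (overall lesion response CR, PR or SD), dated by the latest imaging examination within that assessment. This matches Table 2, row 4, and the protocol, and keeps the SAP's principle of dating by imaging.

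Separately, state whether the last tumor assessment in Note 3 means any scan performed or the last adequate one.

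The cost is a small change of wording. If the programs already follow Table 2, row 4, the rewording alone changes no result. If they follow the text, PFS has to be rerun and some censored times become shorter.

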7.2 Assessment types

7.2.1 Efficacy assessments

Tumor assessments are to be performed for screening purposes and are needed to determine the eligibility of the patient. Last available results of scans performed within 28 days prior to first dose of study drug will be used as baseline values. Negative scans at screening need not be repeated unless warranted by signs and symptoms suggesting disease progression. The assessment data will be collected until disease progression, unacceptable toxicity, death, protocol deviation or other reason that may leads to discontinuation or the end of study.

The following tumor assessments are to be performed and assessed prior to enrollment:

- Abdominal and pelvic triphasic CT or multiphase MRI;
- Chest X-ray (and/or chest CT if disease is present in chest).

To determine eligibility, measurable and non-measurable lesions must be assessed and target lesions identified prior to enrollment. For definition of measurable and target lesions please refer to RECIST 1.1 ([Appendix 1](#))

The same method of assessment and the same technique should be used to characterize each identified and reported lesion at baseline and after every 12 weeks while on-study. All radiology evaluations will be performed initially by the local radiologist.

Details of response assessment are provided in full protocol based on RECIST1.1, and are based exclusively on radiological findings obtained at tumor assessments.

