14.1.27 Sensitivity analyses

This section outlines the possible event and censoring dates for progression, as well as addresses the issues of missing tumor assessments during the study. For instance, if one or more assessment visits are missed prior to the progression event, to what date should the progression event be assigned? And should progression event be ignored if it occurred after a long period of a patient being lost to follow-up? It is important that the protocol and RAP specify the primary analysis in detail with respect to the definition of event and censoring dates and also include a description of one or more sensitivity analyses to be performed.

Based on definitions outlined in [Section 14.1.25](#), and using the draft FDA guideline on endpoints (Clinical Trial Endpoints for the Approval of Cancer Drugs and Biologics, April 2005) as a reference, the following analyses can be considered:

Table 14-5 Options for event dates used in PFS, TTP, duration of response

Situation		Options for end-date (progression or censoring) ¹ (1) = default unless specified differently in the protocol or RAP	Outcome
A	No baseline assessment	(1) Date of randomization/start of treatment ³	Censored
B	Progression at or before next scheduled assessment	(1) Date of progression (2) Date of next scheduled assessment ²	Progressed Progressed
C1	Progression or death after exactly one missing assessment	(1) Date of progression (or death) (2) Date of next scheduled assessment ²	Progressed Progressed
C2	Progression or death after two or more missing assessments	(1) Date of last adequate assessment ² (2) Date of next scheduled assessment ² (3) Date of progression (or death)	Censored Progressed Progressed
D	No progression	(1) Date of last adequate assessment	Censored
E	Treatment discontinuation due to 'Disease progression' without documented progression, i.e. clinical progression based on investigator claim	(1) N/A (2) Date of discontinuation (visit date at which clinical progression was determined)	Ignored Progressed
F	New anticancer therapy given	(1) Date of last adequate assessment (2) Date of secondary anti-cancer therapy (3) Date of secondary anti-cancer therapy (4) N/A	Censored Censored Event Ignored
G	Deaths due to reason other than deterioration of 'Study indication'	(1) Date of last adequate assessment	Censored (only TTP and duration of response)

¹.=Definitions can be found in [Section 14.1.25](#)

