².=After the last adequate tumor assessment. "Date of next scheduled assessment" is defined in Section 14.1.25.

³.=The rare exception to this is if the patient dies no later than the time of the second scheduled assessment as defined in the protocol in which case this is a PFS event at the date of death.

The primary analysis and the sensitivity analyses must be specified in the protocol. Clearly define if and why options (1) are not used for situations C, E and (if applicable) F.

Situations C (C1 and C2): Progression or death after one or more missing assessments: The primary analysis is usually using options (1) for situations C1 and C2, i.e.

- (C1) taking the actual progression or death date, in the case of only one missing assessment.
- (C2) censoring at the date of the last adequate assessment, in the case of two or more consecutive missing assessments.

In the case of two or missing assessments (situation C2), option (3) may be considered jointly with option (1) in situation C1 as sensitivity analysis. A variant of this sensitivity analysis consists of backdating the date of event to the next scheduled assessment as proposed with option (2) in situations C1 and C2.

Situation E: Treatment discontinuation due to ‘Disease progression’ without documented progression: By default, option (1) is used for situation E as patients without documented PD should be followed for progression after discontinuation of treatment. However, option (2) may be used as sensitivity analysis. If progression is claimed based on clinical deterioration instead of tumor assessment by e.g. CT-scan, option (2) may be used for indications with high early progression rate or difficulties to assess the tumor due to clinical deterioration.

Situation F: New cancer therapy given: the handling of this situation must be specified in detail in the protocol. However, option (1), i.e. censoring at last adequate assessment may be used as a default in this case.

Additional suggestions for sensitivity analyses

Other suggestions for additional sensitivity analyses may include analyses to check for potential bias in follow-up schedules for tumor assessments, e.g. by assigning the dates for censoring and events only at scheduled visit dates. The latter could be handled by replacing in [Table 14-5](#) the “Date of last adequate assessment” by the “Date of previous scheduled assessment (from baseline)”, with the following definition:

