14.1.29 Study/project specific decisions

For each study (or project) various issues need to be addressed and specified in the protocol or RAP documentation. Any deviations from protocol must be discussed and defined at the latest in the RAP documentation.

The proposed primary analysis and potential sensitivity analyses should be discussed and agreed with the health authorities and documented in the protocol (or at the latest in the RAP documentation before database lock).

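### The SAP's only PFS analysis counts clinical progression without RECIST progression as an event: a permitted choice, but given no reason and no RECIST-only sensitivity analysis

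*SAP*

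**What the plan says.** **SAP 5.5.2.** The text defines progression by three imaging findings (target-lesion growth, unequivocal non-target progression, new lesions) and dates PFS by the imaging examination. It then refers to Table 2 for the detailed rules. Row 3 of that table takes the case "No progression based on RECIST assessment (i.e. clinical progression based on" the investigator's view, where this ends treatment, and counts it as progression on the discontinuation date. No other PFS event rule is planned.

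**Protocol Appendix 1.** Table 14-5 situation E is the same case: stopping for disease progression "without documented progression, i.e. clinical progression based on investigator claim". Option (1) ignores the claim. Option (2) counts progression at discontinuation. Option (1) is the "default unless specified differently in the protocol or RAP", and 14.1.29 allows the primary and sensitivity analyses to be documented "at the latest in the RAP documentation before database lock".

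**Duties attached to the choice (14.1.27).** The plan is told: "Clearly define if and why options (1) are not used for situations C, E and (if applicable) F". Protocol and RAP should specify event and censoring dates and "also include a description of one or more sensitivity analyses to be performed". Option (2) is offered as a sensitivity analysis, or for indications with high early progression or tumors that are hard to assess.

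**What is planned.** The only efficacy sensitivity analysis is in SAP 5.5.5. It leaves out patients seriously affected by COVID-19 and changes no event or censoring rule. Protocol 10.5.3.5 plans no supportive analysis for secondary objectives. SAP section 7 records no change from the protocol's methods, so no reason is found there either.

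**Note 3 to Table 2.** Row 7 censors an event that follows two or more missed assessments. Note 3 turns this into a fixed gap of more than 24 + 2 weeks since the last tumor assessment.

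**The concern.** Row 3 mixes two kinds of event in one curve: progression seen on a scan, and an open-label clinical judgment that no scan has confirmed. A reader of SAP 5.5.2 who stops at the three imaging criteria would take the result for a RECIST PFS.

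PFS is one of only two secondary endpoints. Protocol 2.2 describes it as the same endpoint as in the global phase 3 study, for which Protocol 1.2.1.2 gives a median of 11.04 months. The documents do not say how that study treated clinical progression. With one rule and no count of row 3 events, nobody can tell how far a comparison depends on the rule. The cases could be found by matching disposition listings to tumor listings, but no planned output shows their number or effect.

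The second issue is linked. The situation E default presumes that patients are followed for progression after stopping, and Note 3 presumes a scan interval. The documents do not settle which scans are taken after treatment.

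**Working it through.** **1. Row 3: inputs.** About 60 patients (Protocol 10.8; SAP section 4). Median PFS 11.04 months (Protocol 1.2.1.2), used only as an illustration. Scans every 12 weeks. Assumed, because the documents give no figure: exponential PFS; a share f = 5, 10 or 15% of events clinical-only; the clinical call uniform over the 12 weeks before the scan that would have shown progression; follow-up of 24 to 48 months.

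**2. Hand check, scans stopping at discontinuation.** S(12) = exp(-ln 2 x 12/11.04) = 0.471. If a share f of events is censored instead, the hazard falls by the factor (1 - f), so S(12) becomes 0.471^(1 - f):
- f = 5%: 0.489 (+1.8 points); median 11.04/0.95 = 11.6 months
- f = 10%: 0.508 (+3.7 points); median 11.04/0.90 = 12.3 months
- f = 15%: 0.527 (+5.6 points); median 11.04/0.85 = 13.0 months

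**3. Paired simulation, n = 60, same patients under both rules, no scans after stopping.**

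| f | Row 3 events (of about 53) | RECIST-only minus row 3 at 12 months, points (5th to 95th percentile) | Difference in median, months |
|---|---|---|---|
| 5% | 2.7 | +1.7 (0 to 4.2) | +0.8 |
| 10% | 5.3 | +3.5 (0.8 to 7.1) | +1.5 |
| 15% | 8.1 | +5.4 (1.8 to 10.0) | +2.2 |

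**4. Which rule is nearer the truth in this model?** The reference is the date on which a scan would have shown progression (12-month PFS 47.1%). Row 3 is 0.2 to 0.6 points low. RECIST-only with censoring at the last scan is 1.5 to 4.8 points high, because the censoring is informative. If scans continue after stopping, RECIST-only recovers the reference and the two rules differ by only 0.2 to 0.6 points.

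**5. Sampling error.** The approximate 95% half-width of one PFS estimate near 50% is 1.96 x sqrt(0.25/60) = 0.127, or about 13 points before any loss to censoring.

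**6. Note 3: reproducing the figure.** Two 12-week intervals plus two 1-week windows: 2 x 84 + 2 x 7 = 182 days = 26 weeks. On 12-weekly scans the longest on-time gap is 84 + 14 = 98 days, and with one scan missed it is 168 + 14 = 182. Neither exceeds 182, so the cut-off does what row 7 intends.

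**7. Which schedule applies after treatment?** Protocol 7.2.1 (12-weekly while on study), Protocol 7.1.5 (end of treatment is not end of study) and SAP Appendix 1 footnotes e and f point to 12-weekly scans until progression. Protocol Table 7-1 and SAP Appendix 1 leave the end-of-treatment scan cell blank and put the only post-treatment scan in the 6-monthly survival column. Protocol 4.1 and another sentence in 7.2.1 can be read as ending collection at discontinuation.

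**8. If the 6-monthly column governs.** Six calendar months is 181 to 184 days. Counted from end of treatment, a gap of 2 or more days since the last scan gives at least 181 + 2 = 183 > 182, so the first on-schedule scan always falls past the cut-off (about 99% of cases averaged over gaps of 0 to 83 days). Counted from first dose, for patients who stop after their first on-treatment scan, the share is about 26 to 27%, or 42 to 44% if the visit must also be at least 30 days after end of treatment. The documents do not state the anchor.

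**The case against.** The strongest reply is that row 3 is authorized. It is option (2) of Table 14-5, and the appendix lets the RAP choose it. That stands: row 3 is no breach, and what is missing is the reason and the second run.

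Several stronger readings are tempting, and the documents do not support them:
- *Row 3 contradicts Protocol 7.2.1.* The words "are based exclusively on radiological findings obtained at tumor assessments" there describe response assessment, not PFS event rules.
- *Row 3 contradicts Protocol 14.1.19.* PFS there runs to "the date of event defined as the first documented progression or death due to any cause", but that is the appendix's general definition, and the same appendix offers option (2) as a PFS end date.
- *Row 3 must repeat 14.1.32.* That section controls who may have disease progression recorded as the reason for stopping. It acts before the analysis.
- *The interim snapshot in Protocol 10.7 depends on this table.* That interim was planned for July 2017 and the second for February 2021 (SAP section 6). The SAP reviewed is dated May 2024, and its history shows PFS rules revised in 2021 and 2024. The point concerns the final analysis.

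It can also be said that the effect rests on an assumed share, lies within sampling error, and concerns a secondary, descriptive endpoint. All true, and this limits the priority. It does not supply the sensitivity analysis that 14.1.27 asks for.

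On Note 3, row 7 itself speaks of assessments not performed as the protocol requires, so an on-schedule scan is not missing by its words. That is right, and it shows the problem: on a 6-monthly schedule, the fixed number in Note 3 would censor what row 7 would not. The patients exposed are only those who stop without clinical progression, start no new anticancer therapy and progress later. Their number has not been estimated.

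**Conclusion.** The point holds as a cheap improvement, not as an error that invalidates the PFS result. The SAP uses a permitted, non-default rule as its only PFS analysis. That rule differs from the SAP's own imaging-based definition and dating, and the two things the protocol asks for with such a choice are absent from the text available to us.

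The size is unknown. With assumed clinical-only shares of 5 to 15%, it is about 2 to 5 points at 12 months if scans stop at discontinuation and under 1 point if they continue.

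A reader might infer that row 3 inflates PFS, or that RECIST-only should be the main analysis. Neither follows. Row 3 adds events and so shortens PFS relative to censoring, and in the model it lies nearer the reference than RECIST-only when scans stop. No test, alpha or power is affected.

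The Note 3 point is secondary and conditional. A reader might infer that 182 days is simply wrong; it is right for 12-weekly scans. It fails only if post-treatment scans follow the 6-monthly column.

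**What to change.** 1. In SAP 5.5.2, state why situation E option (2) is used. Add one RECIST-only PFS sensitivity analysis (option (1): the clinical claim is ignored, and later documented progression or death counts under the other rows) to the final analysis. Report the number of row 3 events. Row 3 may stay the main rule; that is the sponsor's choice.
2. Reconcile Protocol 4.1, 7.2.1, Table 7-1 and footnotes e and f on post-treatment scans. Apply row 7 by counting scheduled assessments actually missed, so that progression on an on-schedule scan is an event at its scan date.

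**Cost.** A few sentences, one extra Kaplan-Meier run and one count. Part 1 leaves the main estimate unchanged if row 3 stays. Part 2 changes it only if post-treatment scans were in fact taken 6-monthly. The downside is that, if scans stop at discontinuation, informative censoring may bias the RECIST-only result upward, so it must be read beside the row 3 result and not in place of it.
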